3.3 Clinical Evidence to Date

3.3.1 SmartBone

Pre- and post-market clinical investigations to date using SmartBone were performed only in the field of oral, maxillofacial and cranial surgery. The rationale behind this focus was that findings regarding performance and safety of a bone graft in said fields can be transferred to the use of the device in all orthopedic applications, but that vice-versa conclusions are not possible. In the following, clinical study data regarding SmartBone are summarized.

Study design	No. of pat.	Aim	Setup	Results
Single-centre, non-randomized, comparative clinical trial [37].	5	Assessment of complete in vivo biocompatibility and efficacy.	Comparison of the non-CE marked device with its CE marked raw material component Tutobone (Tutogen, Germany).	Histological analyses confirmed osteointegration and remodeling capabilities.
Post-market clinical follow-up. Randomized, non-blinded, multi-centric clinical trial (not published yet).	44	Confirm clinical performance and safety throughout a meaningful observation period.	17 investigators performed surgeries in oral, maxillofacial and cranial districts. Quantitative assessment of bone regeneration based on evaluation of grafted volume evident on radiographs.	27 patients monitored over the entire time frame (1 year). Out of the total of 44 patients: 12 cases showed optimal regeneration. 29 showed good regeneration. 3 showed medium regeneration. No failures, no accidents, nor adverse events nor poor results were recorded.
Monocentric cohort study [54].	62	Confirm safety, performance and acceptability of identified residual risks	Monitoring safety and performance outcome using quantitative assessment of bone regeneration based on evaluation of grafted volume evident on radiographs.	60 patients monitored over the entire time frame (>1.5 years). 55 cases showed optimal regeneration. 1 case with good regeneration. 3 cases with poor regeneration. 1 case with a reported failure for dehiscence. No further failures, no accidents, nor adverse events nor poor results were recorded. The clinical data confirmed safety and performance of the device and showed acceptability of residual risk.

Histological investigation [55].	10	Assess the mechanism of action of the device histologically.	Collection of tissue biopsies from clinical cases allowing easy and precise sample collection. Histomorphometric analysis and bone-particle conductivity index calculation.	Based on the analysis of 6 histological images it was concluded that the bone graft shows about 35 – 40% substitution at about 4 – 8 months and complete substitution after about 2 years. No inflammatory cells were detected, confirming full biocompatibility of the medical device.
Multicenter prospective clinical trial (not published yet)	58	Evaluation of the newly-formed tissue, correlating clinical and histological results to the sinus cavity size and conformation.	Transcrestal sinus floor elevation performed in atrophic ridges. Cone beam computed tomography 10 days and 6 months after surgery. After 6 months a bone-core biopsy was harvested. Histomorphometric analysis was conducted.	56 cases showed good or optimal regeneration. 2 cases with failure for dehiscence. No further failures, no accidents, nor adverse events nor poor results were recorded.
Monocentric cohort study (not published yet)	10	Histomorphometric evaluation.	Alveolar preservation after tooth-extraction. Collection of biopsies 4 months after implantation. Comparison of histological images with known cases treated with other commercially available bone substitutes.	Biopsies collected at 4 months post-implantation showed the contemporaneous presence of SmartBone, new bone and fibrous tissue with formation of new vessels. Bone ECM molecules were highly expressed in the newly formed bone and osteoblasts were visible on the device's surfaces. No failures, no accidents, nor adverse events nor poor results were recorded.

3.3.2 Autograft Scaffolds for ACL-Graft Fixation

Kim et al. [56] prospectively reviewed 81 patients who had undergone ACL-reconstruction with an Achilles tendon allograft using a bioabsorbable interference screw (group I) or an autogenous bone plug harvested from the tibial bone tunnel (group P) for tibial graft fixation. Patients and outcome-assessors were blinded to group assignment. After an average follow-up of 7.5 years, complication rate in group P was significantly less frequent than in group I (6 vs. 14) and tunnel widening, assessed as cross-sectional area on MRI, averaged 15% in group P and 38% in group I ($p = 0.017$). No significant changes for patient subjective outcome scores

and stability were detected. The authors deemed the use of autograft bone plugs for graft-fixation a reasonable option for ACL-reconstruction with Achilles tendon allograft.

3.3.3 Xenograft Scaffolds for ACL-Graft Fixation

The bovine bone matrix SmartBone consists of is a CE-marked product (Tutobone) by Tutogen, Germany. In a randomized controlled trial, Jagodzinski et al. [57] used Tutobone, shaped into a conical block, for tibial press-fit fixation of the hamstring autograft in ACL-reconstruction. This approach was compared to the traditional technique using bioresorbable interference screw fixation, in terms of clinical outcome and BTW. At the proximal section of the tibial bone tunnel, the tunnel diameter was significantly smaller for the press-fit group at 3, 6, 12 and 24 months follow-up. No significant differences were detected for IKDC-, Tegner-, Lysholm score and knee stability between the two groups. No intra- or postoperative complications were reported.

3.3.4 Adverse Device Effects

In 2008, Konan et al. [58] summarized the literature concerning adverse device effects associated with the use of bioabsorbable interference screws in ACL-reconstruction. Adverse device effects identified, related to composite screws containing a part bioceramic (β -TCP/HA), were:

- Screw breakage during insertion
- Subcutaneous cyst formation (cured within the following 3 months)

Tecklenburg et al. [59] evaluated the clinical outcome of ACL-reconstruction using hydroxyapatite composite screws, β -TCP composite screws and allograft interference screws in a total of 60 patients. There was no inflammatory response noted in any patients.

3.4 Rationale for the Intended Purpose in Study

The clinical outcome of ACL-reconstruction depends on the successful integration of the tendon-graft into the host bone close to the attachment site of the native ACL [60-62]. The OCS is enlaced into the tendon-suture construct and provides an osteoconductive / osteoinductive environment at the articular aperture of the bone tunnel. The design maximizes the contact area between tendon and osteoconductive surface (Bone/HA). Different to the application of interference screws, graft insertion exerts minimal stress on the insert and allows the use of highly porous material. Enhanced bone-tendon integration should reduce graft micromotion and increase the repair strength of the reconstructed ACL. This in turn should reduce the rate of graft failure and the incidence of tunnel widening.

3.5 Explanation for Choice of Comparator

The active comparator in the current study will be the standard ACL-reconstruction technique used at Balgrist University Hospital.

3.6 Risk / Benefits

Since the OCS is an approved, CE-marked device, product related risks like biocompatibility, shelf-life et cetera were excluded from the internally conducted risk assessment and possible adverse effects of the product can be seen in the instruction for use.

However a careful and detailed risk assessment was performed according to EN ISO 14971:2013-04 to also take overall - not only product related risks into account.

To identify and evaluate the risks a Failure Mode and Effects Analysis (FMEA) was performed, based on EN ISO 14971:2013-04 Annex C informative guideline.

The full FMEA can be delivered upon request. In the following the results of the investigation are summarized. Identified risks in *italic*.

Clinical study related risks

- *Surgical team (surgeons, staff) is not introduced to clinical study procedure (device is not used according to study protocol).* This risk has been minimized by several pre-clinical cadaver tests, where the full intervention was carried out, documented and analyzed with the involved team. (KEK-ZH-Nr. 2015-0372, Developing a novel surgical procedure for improved ACL reconstruction).
- *Logistical flow from producer to patient does not work.* Involved staff is informed and used to handling and storage conditions of the different medical products used for this study (OCS, sutures).
- *Soft tissue bridging during graft insertion.* In performed cadaver tests a possible soft tissue bridging which can occur during graft insertion through the medial portal did not occur. Since the graft insertion is reversible until knots are fastened this issue can be solved intraoperatively.
- *OCS breaks during graft insertion.* *In-vitro* experiments were performed in order to assess device strength during surgical insertion. For femoral pull-in of the construct, a force of 250N was applied resembling maximal achievable voluntary one-handed force. Subsequently, the construct was extracted and inspected for damage. None of the samples showed damage to the OCS.
- *ACL loads during rehabilitation lead to damage to OCS and to subsequent release of particles into the joint capsule.* The laboratory of Orthopedic Biomechanics at ETH Zurich performed mechanical *in-vitro* testing on the construct under study in porcine knees. The experiment included high load – low cycle testing, simulating out of the ordinary situations such as stumbling or jumping, as well as low load – high cycle testing, simulating the long term mechanical environment during rehabilitation. The OCS performed well in all tests with no signs of abrasion particles being released from the construct.
- *OCS inserted into the tendon-graft reduces the fatigue life of the graft-construct.* The material properties of the OCS highly differ from the material properties of the surrounding tendon. The OCS might damage the tendon or the suspension suture and accelerate fatigue failure of the construct. Comparing the fatigue life of the construct with OCS and without OCS revealed no such effect.

The overall risk of this study is therefore stated as very low and has been evaluated acceptable, the expected benefits outweigh the minimized residual risk.

Expected Benefits:

- Faster healing of soft-tissue to bone (up to 3-times more tendon to bone surface area)
- Stronger secondary fixation by having a „bony bridge“
- Reduced tunnel widening due to faster secondary fixation (bone to bone) and windshield wiper effect.
- A successful outcome of this study would have a big impact in an improved ACL reconstruction. Further studies for a tibial (femoral & tibial) solution could be carried out on the basis of this study.

3.6.1 Radiological Assessment Related Risks

The mean volume CT dose index and the dose-length product of one CT-scan of the knee are approximately 9.8 mGy and 189 mGy*cm respectively. Using an effective dose conversion

coefficient of 0.0004 mSv/(mGy*cm) for the knee of an adult subject [63] yields an effective radiation dose of 0.0756 mSv per examination.

According to the reference table provided by Swissethics, one plain radiography examination of the knee in anterior-posterior direction yields an effective radiation dose of 0.015 mSv [64].

The table below shows the calculation of the total effective radiation dose each participant is exposed to by the two measurement modalities used in the current study [65].

Measurement modality	Effective dose per examination [Millisievert]	Number of examinations per subject	Total effective radiation dose per subject [Millisievert]
Computed Tomography	0.0756	3	0.2268
Plain Radiology	0.015	5	0.075
Total exposure			0.3018

3.6.2 Anticipated Adverse Device Effects

Anticipated adverse device effects based in part on the literature search described above are the following.

- Subcutaneous cyst formation
- Intratunnel cyst formation [66]

Subcutaneous cysts usually reside over time and are easily manageable surgically [66, 67].

Intratunnel cysts are related to the effect of BTW and are therefore subject of the current investigation.

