5 STUDY OUTCOMES

5.1 Primary Outcome

The primary outcome variable of this study is the relative change of the CT evaluated femoral bone tunnel volume from baseline to follow-up at 12 months.

As the primary objective of the use of the OCS is to reduce tunnel widening by promoting bony ingrowth into the bone tunnel, the relative change of bone tunnel volume over time is an appropriate measure to quantitatively assess this effect. Assessing relative changes as opposed to absolute values negates the potential for bias by different tunnel drill sizes used in the two treatment arms potentially influencing the absolute ossification/de-ossification. In quantifying bone tunnel size, CT measurements provide substantially more reliable means than plain radiography or magnetic resonance imaging [50, 68].

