5.3.3 Intra-Patient Comparison of Ossification

The intervention group will be additionally assessed in an intra-patient comparison model [51]. Using the available CT data, the tibial bone tunnel volume will be calculated using the same method as for the femoral bone tunnel volume described below. The relative change of the two parameters will be compared.

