9 STUDY ASSESSMENTS

9.1 Study Flow Chart

9.2 Assessments of Outcomes

9.2.1 Assessment of Primary Outcome

Bone tunnel volume will be assessed on CT. CT-scanning will be overseen by an experienced radiologist. The procedure (including pregnancy testing) is described in more detail in ACLROCS_WI_CTS defense. The DICOM (Digital Imaging and Communications in Medicine) series are converted into a single volume and cropped to include the distal femur. Subsequently, the follow-up volumes of each patient are volumetrically registered to the baseline volume by using a rigid affine mutual information algorithm [83]. An intensity-based mask of each volume is created and cropped to contain only the femoral bone tunnel. The voxel-based volume of each follow-up mask is determined and compared to the baseline volume. The procedure is described in detail in ACLROCS_WI_FemBoneTunVolCalc.

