9.2.5 Assessment of Safety Outcomes

9.2.5.1 Adverse Events

Intra-operative complications (if any) will be recorded on the eCRF. Self-reported AEs will be assessed by interviewing the patient. The following question will be used:

“Hatten Sie im Zusammenhang mit Ihrer Knieoperation irgendwelche nennenswerten medizinischen Probleme?”

Also any out of window visit or unexpected finding will be recorded. The following adverse event information will be recorded:

- Adverse event term
- Date of onset
- Date of resolution/Duration
- Severity (Subjective assessment by PI)
- Seriousness
- Relationship with surgical intervention
- Relationship with device under study
- Actions taken in response
- Outcome of the adverse event

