10 SAFETY

10.1 Medical Device Category A studies

10.1.1 Definition and Assessment of safety related events

Adverse Event (AE)

Any untoward medical occurrence, unintended disease or injury or any untoward clinical signs (including an abnormal laboratory finding) in participants, users or other persons whether or not related to the investigational medical device [ISO 14155: 3.2].

Serious Adverse Event (SAE)

Adverse event that:

- results in death, or
- led to a serious deterioration in health that either:
 - results in a life-threatening illness or injury, or
 - results in a permanent impairment of a body structure or a body function, or
 - required in-patient or prolonged hospitalisation, or
 - results in medical or surgical intervention to prevent life threatening illness, or
- led to fetal distress, death or a congenital abnormality or birth defect. [ISO 14155: 3.37].

Health hazards that require measures

Findings that may require additional action are:

- Persistent anterior knee pain
- Septic arthritis
- Arthrofibrosis
- Graft rupture
- Aseptic effusion
- Subcutaneous cyst

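### Intratunnel cyst is a declared anticipated device effect, but no outcome or imaging item identifies or counts it, so the safety tables may under-report it

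*Combined protocol and SAP*

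**What the plan says.** **The declared effect.** Section 3.6.2 lists two anticipated adverse device effects: subcutaneous cyst and intratunnel cyst. It describes the first as manageable. It assigns the second to the efficacy question: "Intratunnel cysts are related to the effect of BTW and are therefore subject of the current investigation".

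**What is measured on images.** The primary outcome in 5.1 is the "relative change of the CT evaluated femoral bone tunnel volume from baseline to follow-up at 12 months". Section 9.2.1 describes how it is obtained: "An intensity-based mask of each volume is created and cropped to contain only the femoral bone tunnel". Plain films give one maximum width of the femoral tunnel (5.3.4, 9.2.3). Tibial tunnel volume appears only in 5.3.3 and 11.4.3.1, and for one arm: "The intervention group will be additionally assessed in an intra-patient comparison model". Section 5.3.2 samples a density line across the scaffold on one selected slice.

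**How safety is recorded.** Post-operative adverse events are recorded at each follow-up visit (5.4, 9.3.3 to 9.3.5). Section 9.2.5.1 specifies intra-operative complications, one interview question, and this addition: "Also any out of window visit or unexpected finding will be recorded". It also asks for each event's relationship to the device. Section 6.3.2 says that the practitioner who views the images at follow-up and for safety cannot be blinded. The list of findings that may need action in 10.1.1 includes "Subcutaneous cyst" but not the intratunnel cyst. Section 11.4.6 tabulates adverse events by group, descriptively.

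**The concern.** The safety objective in 4.4 is about how often complications occur and how severe they are. For one of the two effects that the sponsor itself anticipates, the protocol gives no definition, no instruction to look and no count. Section 3.6.2 implies that studying tunnel widening covers it, but a volume or a width does not say whether a cyst is present.

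A cyst without symptoms is not an intra-operative event, and a patient cannot report it at interview. Whether it enters the adverse event record then depends on whether the person viewing the images regards it as an adverse event, as an unexpected finding, or as part of the widening already measured for efficacy. That person knows the allocation, so the threshold for recording may differ between arms.

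This matters because earlier clinical investigations of the product were confined to oral, maxillofacial and cranial surgery (3.3.1). A low count in this trial would be among the first clinical safety data for the scaffold in this use, and readers would give it weight.

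The same gap exists for the scaffold after surgery. Section 3.6 identifies the risk that "ACL loads during rehabilitation lead to damage to OCS and to subsequent release of particles into the joint capsule" and answers it with in-vitro testing. No outcome records whether the scaffold is intact and in place on the follow-up CTs.

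**Working it through.** **1. Is a cyst counted anywhere?**

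| Place | What it yields | Identifies a cyst? |
|---|---|---|
| 5.1, 9.2.1 | Femoral tunnel volume from an intensity mask | No; a cyst can at most add to the volume |
| 5.3.4, 9.2.3 | Largest femoral tunnel width on plain film | No |
| 5.3.3, 11.4.3.1 | Tibial tunnel volume, intervention arm only | No, and no control value |
| 5.3.2 | Density profile along one line | No |
| 9.2.5.1 interview | Problems the patient notices | Only if symptomatic |
| 9.2.5.1 other findings | Unexpected findings | Possibly, at discretion |
| 5.4, 9.3.3 to 9.3.5, 10.1.1 definition | Any adverse event at a visit | Possibly, at discretion |
| 10.1.1 list | Findings that may need action | Not listed |

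The tibial row matters because the source cited in 3.6.2 for intratunnel cysts is, by its title in the reference list, about tibial tunnel and pretibial cysts. On that side not even a volume is compared between arms.

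**2. The plan's sample size (11.2).** Difference 20, SD 25.175, two-sided alpha 0.05, power 0.8:

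n = 2 × (1.960 + 0.842)² × 25.175² / 20² = 24.9, so 25 per group. With 10% drop-out, 25 / 0.9 = 27.8, so 28 per group and 56 in total. This reproduces the plan. (The t-distribution version gives 25.87, so 26; nothing here depends on that.) The denominators below are therefore 28 randomized and 25 after the planned drop-out. Section 8.8 also removes patients with complications during surgery with the device, so the number assessed could be lower.

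**3. What a zero count would mean if cysts were looked for in every patient.** The exact two-sided 95% upper limit for 0 of n is 1 − 0.025^(1/n):

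- n = 28: 1 − 0.025^(1/28) = 12.3%
- n = 25: 1 − 0.025^(1/25) = 13.7%

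The one-sided 95% limits, 1 − 0.05^(1/n), are 10.1% and 11.3%.

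**4. What it means under discretionary capture.** Let s be the chance that a cyst present on CT is recorded. The table then estimates s × p, not the true rate p, and the limit on p becomes the limit in step 3 divided by s. The documents do not give s, so these values are assumptions:

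| s | 0 of 28 | 0 of 25 |
|---|---|---|
| 1 | 12.3% | 13.7% |
| 0.5 | 24.7% | 27.4% |
| 0.25 | 49.4% | 54.9% |

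With s unknown, no limit can be stated. If s differs between arms, the ratio of recorded rates is the true ratio multiplied by s(intervention) / s(control).

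**5. Would there be anything to find?** The documents give no cyst rate. Under assumed rates, the chance of at least one cyst among 28 patients, 1 − (1 − p)^28, is 25% at p = 1%, 76% at 5%, 95% at 10% and 99.8% at 20%.

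**6. Images available.** Each patient has three CTs (3.6.1), two of them at follow-up (4.5 and 12 months). With full retention that is 28 × 2 = 56 follow-up CTs per arm.

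**The case against.** A reader might infer that the plan has no route at all for a CT-detected cyst, so that the safety tables will show none even when the scans do. The documents do not support that. Section 5.4 records post-operative adverse events at each visit without restricting their source. Sections 9.3.3 to 9.3.5 have the investigator record any potential event at the examination. The definition in 10.1.1 does not exclude imaging findings, images are viewed for safety (6.3.2), and 11.4.6 tabulates the events. A cyst that is noticed can reach the table.

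Nor does 9.2.5.1 say that an anticipated effect cannot be an unexpected finding. That reading is possible but is not stated, and the visit-based route does not depend on the word.

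The list in 10.1.1 is not the list of events to be counted. It concerns findings that may need action, and 10.1.2 attaches a 2-day report to health hazards that require measures. Omission from it does not keep a cyst out of the tables. It is only an unexplained mismatch with 3.6.2.

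A reader might also infer that scaffold breakage is unrecorded. Breakage during insertion is an intra-operative complication and is captured. What lacks an item is later fracture or displacement. The documents do not establish that particles in the joint would be visible on CT, so that part cannot be pressed.

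Finally, the eCRF and the imaging work instructions are not among the documents, and a reading item may exist there.

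All of this stands, and it limits the point. It does not supply a definition, an instruction to look or a denominator.

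**Conclusion.** The plan declares intratunnel cyst an anticipated device effect and says that it is being investigated, but the protocol contains no outcome or prespecified imaging item that identifies or counts it. Tunnel volume cannot replace one. Capture as an adverse event is possible but discretionary, made by someone who knows the allocation, and without a count of scans assessed. The by-arm tables may therefore under-report cysts, and a low or zero figure could not be read as absence.

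The size is best stated as what would be lost. A looked-for 0 of 28 would exclude rates above 12.3%, and 0 of 25 rates above 13.7%. Without systematic reading neither statement can be made. These are generic binomial limits; they do not estimate how many cysts would be missed, because the documents give neither a cyst rate nor a recording rate.

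The conclusion rests on the protocol text alone and assumes that no cyst item sits in the eCRF or work instructions. The primary analysis is not affected. The change is worth making because the scans are already scheduled and already viewed.

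**What to change.** - **Add a structured imaging item** to 5.4 and 9.2.5, completed at each scheduled follow-up CT by the practitioner who already views the images. For both arms and both tunnels: intratunnel cyst present or absent, and largest diameter. For the intervention arm: scaffold intact, fractured or displaced.
- **State how a CT-detected cyst is classified**, that is, whether it is also an adverse event.
- **Tabulate in 11.4.6** by arm and visit, with scans assessed as the denominator, kept apart from symptomatic adverse events.
- **State that the reader is unblinded** (6.3.2), so that any difference between arms is read with that in mind.
- **Reconcile 3.6.2 with the list in 10.1.1.** Whether to list the intratunnel cyst there is for the sponsor to decide, knowing that 10.1.2 ties health hazards that require measures to reporting within 2 days.

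The cost is one short extra eCRF page and some reading time. No new imaging or radiation is needed. The downside is more reported findings, some of which may be silent.
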